3	5	8	40	72.00	60.00

Note – the first 6 evaluable patients enrolled will be treated at Dose Level 1 Please refer to section 10.0

Version 09/11/2025 page 10 of 63

SCHEDULE OF ACTIVITIES

	Screening	Pre- treatment ⁸	Radiation	1-2 Weeks post RT	6-8 Weeks post RT	3 Mo post RT ¹	6 Mo post RT ¹	9 Mo post RT ¹	12 Mo post RT ¹	
Informed consent	X^2									
H&P / PS / weight / DRE ¹³	X^2		X^3	X	X	X	X	X	X	
MRI pelvis ⁴	X^2				X	5	X	X	X	
CT chest / abdomen / pelvis with contrast ⁶	X^2				X ⁶		X	X	X	
Endoscopy ⁷	X^2				X	15				
OPTIONAL biopsy	$X^{2, 15}$				Х	ζ				
CBC w/diff	X^2	X^2			X^9		X			
CMP	X^2	\mathbf{X}^2			X^9		X			
CEA		X			X^9		X			
SCCA		X			X ⁹		X			
CRP		X			X ⁹		X			
LDH		X			X ⁹		X			
Pregnancy test	$X^{10,11}$									
Radiation therapy			X^{12}							
EORTC QLQ-C30		X		X		X	X	X	X	
EORTC QLQ-C29		X		X		X	X	X	X	
Adverse events		X	X^3	X	X	X	X	X	X	

- 1. +/- 2 weeks
- 2. No more than 60 days prior to registration. Screening and baseline labs can be the same draw provided the timing aligns.
- 3. Performed once during radiation therapy.
- 4. Cross-sectional imaging with either MRI or CT is acceptable.
- 5. MRI pelvis and CT chest/abdomen with contrast may be obtained 6 weeks to 3 months after radiation completion with a RECIST read at 3 months only.
- 6. If PET/CT scan is done, then CT chest/abdomen/pelvis not required.
- 7. Endoscopy with colonoscopy, sigmoidoscopy, or proctoscopy will be performed if feasible after screening.
- 8. Baseline labs and QOL assessments should be performed within 30 days of radiation therapy.
- 9. Labs should be drawn once 6 weeks to 3 months after radiation completion but should be drawn before surgery if the patient undergoes salvage surgery.
- 10. Mandatory for women of childbearing potential.
- 11. Within 14 days of registration.
- 12. 5 fractions over 1 week.
- 13. DRE only to be done if feasible.15. OPTIONAL endoscopy with biopsy performed 6 weeks to 3 months after completion of RT; for research purposes only.
- 15. OPTIONAL screening biopsy to be performed at time of baseline SOC endoscopy.

Version 09/11/2025 page 11 of 63

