5.2.1 Dose-Limiting Toxicities (DLTs)

Dose-limiting toxicities (DLTs) are defined as any toxicity listed below that occurs within 6 months from the start of treatment and is considered possibly, probably, or definitely related to proton reirradiation:

- Any grade 5 toxicities
- Any grade 4-5 GI toxicities
- Bowel obstruction
- Grade 3-5
 - o Diarrhea
 - o Anal, colonic, or bowel ulcers
 - o Bladder perforation
 - Any fistula formation
 - o Peripheral/motor sensatory neuropathy of the pelvis above baseline
 - Osteonecrosis/soft tissue necrosis
 - Radiation dermatitis
 - Hematuria
 - o Hematochezia
 - o Bowel/pelvic hemorrhage
 - Reproductive tract toxicity

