6.1 WU PI Reporting Requirements

6.1.1 Reporting to the Human Research Protection Office (HRPO) at Washington University

Reporting will be conducted in accordance with Washington University IRB Policies.

Pre-approval of all protocol exceptions must be obtained prior to implementing the change.

6.1.2 Reporting to the Quality Assurance and Safety Monitoring Committee (QASMC) at Washington University

The PI (or designee) is required to notify the QASMC of any unanticipated problems involving risks to participants or others occurring at WU or any BJH or SLCH institution that has been reported to and acknowledged by HRPO.

Version 09/11/2025 page 30 of 63

(Unanticipated problems reported to HRPO and withdrawn during the review process need not be reported to QASMC.)

QASMC must be notified within **10 days** of receipt of IRB acknowledgment via email to [contact]. Submission to QASMC must include the myIRB form and any supporting documentation sent with the form.

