9 DATA AND SAFETY MONITORING

In compliance with the Washington University Institutional Data and Safety Monitoring Plan, the Principal Investigator will provide a Data and Safety Monitoring (DSM) report to the Washington University Quality Assurance and Safety Monitoring Committee (QASMC) semi-annually.

. The first report is required either 30 days after the enrollment of the 5th participant (if sooner than 6 months after study activation) or 6 months after study activation (provided at least one patient has been enrolled; if zero patients have been enrolled at the 6-month mark, the first report will be required one year after accrual opens provided at least one patient has been enrolled).

The Principal Investigator will review all patient data at least monthly and provide a semi-annual report to the Quality Assurance and Safety Monitoring Committee (QASMC). This report will include:

- Study demographic information (local protocol number, protocol title, list of primary study team members, study sites, primary and secondary sponsors, IND/IDE status, date of most recent QA audit, and study status and history (including activation and suspension dates)
- Accrual information, including study-wide target accrual and actual accrual, anticipated and/or actual accrual end date, and accrual by year by site (if applicable)
- Subject status information presented in both cumulative format (total number of subjects who consented, enrolled, screen failed, started intervention, discontinued

Version 09/11/2025 page 38 of 63

- intervention, went off study, expired) and current format (number of subjects in screening, on intervention, in follow-up, or off study at time of report)
- Protocol objectives and the number of participants who are evaluable for each objective
- History of study (including summaries of substantive amendments, accrual suspensions and reasons, protocol exceptions, errors, and breaches of confidentiality)
- Summary of exceptions, noncompliance reports, and unanticipated problems reported to the IRB
- Early stopping rules and data describing whether the stopping rules have been met (if applicable)
- Interim analysis plans and the results of the interim analysis (if applicable)
- Separate SAE and worst grade toxicity tables, each separated by site (if applicable) and arm/cohort/dose level (if applicable)
- Participant-level response and survival data by arm/cohort/dose level (if applicable)

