- Summary of specimen collection (percentage of participants who have had specimens collected at each required time point)
- Abstract submissions/publications
- Summary of any recent literature that may affect the safety of participants or the ethics of the study

•

The study principal investigator and Research Patient Coordinator will monitor for serious toxicities on an ongoing basis. Once the principal investigator or Research Patient Coordinator becomes aware of an adverse event, the AE will be reported to the HRPO and QASMC according to institutional guidelines.

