In order to account for the possibility of poor initial outcomes we will employ a run-in of 6 patients, meaning that the minimum number of treated patients will be 6. If after these 6 patients, or any other time during the trial, the lowest dose level has a posterior probability higher than 40% then the trial will stop.

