10.2.1 Workflow

The first patient will be enrolled on the trial and treated at PTV total dose 30 Gy, which is one dose level below the hypothesized MTD. That patient will be entered into the titecrm.sas program and follow-up will begin from start of treatment.

For the purposes of this trial, the patient will be followed from start of treatment until the patient completes 12months of follow-up, has a DLT, or is lost to follow-up. If any of these endpoints occur, the statistician will be notified and the date corresponding to the event will be entered into the program. While there is a maximum follow-up of 6 months for observation of possible toxicities, sometimes patients have a delay in their treatment resulting in the need for a prolonged observation period. This delay will be accounted for, as needed, for this study to ensure a complete 6-month follow-up.

When a new patient is enrolled on the trial, the statistician will be notified of the date of enrollment. At that time the statistician will update the follow-up for all patients currently on the trial and determine the dose that will be administered for the new patient. We will utilize the cumulative time of exposure method, which will allow the contribution of patients with no DLT at this time to be partially weighted consistent with their time observed. We will also utilize the weight function to place more emphasis on the first 6 months follow-up (75% weight) compared to the last 3 months of follow-up (25% weight). At this point, the program provides a summary of the number of patients treated at each dose so far, along with the number of DLTs that have occurred. The posterior probability and 95% credible intervals of dose limiting toxicity for each dose level is calculated. At this point, the model determines the dose level that has an estimated toxicity rate closest to 35% within the 5% admissible margin.

The newly enrolled patient will be enrolled in the corresponding dose level if that dose level is within one dose level from the dose level the most current patient is enrolled on. If the suggested dose level is more than one dose level from the current dose level the next patient will be enrolled on the dose level that is closest to the current level in the direction of the dose level determined from the estimated

Version 09/11/2025 page 42 of 63

posterior probability. This continues until the trial has accrued all 20 patients or, if after 6 patients are enrolled, the estimated posterior.

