APPENDIX E: Reporting Timelines

Expedited Reporting Timelines					
Event	HRPO	QASMC			
Unanticipated problem involving risk to participants or others	Report within 10 working days. If the event results in the death of a participant enrolled at WU/BJH/SLCH, report within 1 working day.	Report via email after IRB acknowledgment			
Major deviation	Report within 10 working days. If the event results in the death of a participant enrolled at WU/BJH/SLCH, report within 1 working day.				
A series of minor deviations that are being reported as a continuing noncompliance	Report within 10 working days.				
Protocol exception	Approval must be obtained prior to implementing the change				
Complaints	If the complaint reveals an unanticipated problem involving risks to participants or others OR noncompliance, report within 10 working days. If the event results in the death of a participant enrolled at WU/BJH/SLCH, report within 1 working day. Otherwise, report at the time of continuing review.				
Breach of confidentiality Incarceration	Within 10 working days. If withdrawing the participant poses a safety issue, report within 10 working days.				
	If withdrawing the participant does not represent a safety issue and the patient will be withdrawn, report at continuing review.				

Routine Reporting Timelines						
Event	HRPO	QASMC				
Adverse event or SAE that does not require expedited reporting	If they do not meet the definition of an unanticipated problem involving risks to participants or others, report summary information at the time of continuing review	Adverse events will be reported in the toxicity table in the DSM report which is typically due every 6 months.				
Minor deviation	Report summary information at the time of continuing review.					
Complaints	If the complaint reveals an unanticipated problem involving risks to participants or others OR noncompliance, report within 10 working days. If the event results in the death of a participant enrolled at WU/BJH/SLCH, report within 1					

Version 09/11/2025 page 60 of 63

	working day. Otherwise, report at the time of	
	continuing review.	
Incarceration	If withdrawing the participant poses a safety	
	issue, report within 10 working days.	
	If withdrawing the participant does not represent a safety issue and the patient will be withdrawn,	
	report at continuing review.	

Version 09/11/2025 page 61 of 63

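### A treatment-related death counts as one ordinary DLT, and nothing in the plan holds the next treatment start or requires a decision first

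*Combined protocol and SAP*

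**What the plan says.** **How a death enters the design.** Section 5.2.1 opens its DLT list with "Any grade 5 toxicities", provided the event falls within 6 months of starting treatment and is at least possibly related. Grade 3 diarrhea is in the same list. When a DLT occurs, Section 10.2.1 says "the statistician will be notified and the date corresponding to the event will be entered into the program". The next enrolled patient then gets the level with an estimate closest to 35%, within a 5-point margin and at most one level away from the last patient. The Schema note adds that "the first 6 evaluable patients enrolled will be treated at Dose Level 1".

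**When the trial must stop.** Section 10.1.2 sets a run-in of six and one rule, to be applied then or at any other time: if "the lowest dose level has a posterior probability higher than 40% then the trial will stop". Appendix F lists this as the only early stopping rule and reports no interim toxicity analysis.

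**What oversight exists.**
- Section 9: "The Principal Investigator will review all patient data at least monthly". The first QASMC report is due 30 days after the fifth enrollment if that comes before month 6 from activation, and otherwise at month 6 once a patient has enrolled; reports are semi-annual after that. They include toxicity tables by dose level and the status of the stopping rule. Appendix F adds cause of death by patient.
- Section 9, on any adverse event: "the AE will be reported to the HRPO and QASMC according to institutional guidelines".
- Appendix E, for an unanticipated problem or major deviation: "If the event results in the death of a participant enrolled at WU/BJH/SLCH, report within 1 working day". This report goes to the HRPO.
- Section 6.1.2: the investigator is "required to notify the QASMC of any unanticipated problems involving risks to participants or others", within 10 days of IRB acknowledgment.
- Section 5.7: the cancer center may close the study.

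**The concern.** This is a dose-escalation study of high-dose-per-fraction reirradiation in pelvises that have already been irradiated. Section 1.7.3 says organ tolerances for such schedules are not yet known. A 35% target may be reasonable for a list made up mostly of grade 3 events. Nothing in the plan says that a treatment-related death should be traded off at that rate.

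The 40% rule asks whether the lowest dose is too toxic on all DLTs combined. It does not ask whether the trial should continue after a death. If no other step forces that question, the next patient can be treated after a related death, possibly at a higher dose, before anyone has had to decide that this is acceptable.

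**Working it through.** **1. Is any step tied to dosing?** This part needs no model.

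| Step | Triggered by a related death? | Holds the next start or requires a decision? |
|---|---|---|
| DLT date to the statistician (10.2.1) | Yes, if within 6 months | No; it updates the estimate |
| 40% rule (10.1.2, Appendix F) | Only through the pooled estimate | Yes, if the threshold is crossed |
| Monthly investigator review (9) | No; by calendar | No |
| QASMC reports (9) | No; by calendar | No |
| AE reporting under institutional guidelines (9) | Yes | Not stated |
| HRPO within 1 working day (Appendix E) | If an unanticipated problem or major deviation | No |
| QASMC notice (6.1.2) | If an unanticipated problem acknowledged by HRPO | No |
| Closure by the cancer center (5.7) | No trigger given | Discretionary |

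The only mandatory stop is the 40% rule.

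**2. The plan's own figures.** The threshold is consistent: 35% + 5% = 40%. Section 10.2 also reports about 95% of simulated trials completing. This can be neither confirmed nor refuted, because the model, prior, true rates and accrual behind it are not given. Over three assumed models and three sets of true rates, completion ran from 48% to 95%.

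**3. What would the 40% rule do after a death?**

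From the documents: target 0.35; stop above 0.40; six patients at Level 1; one-level steps; initial rates 0.25/0.30/0.35/0.40 for Levels -1, 1, 2, 3 (Section 10.2 table; Section 10.1.1 gives a different range, 0.05 to 0.25 over five levels).

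Assumed: b ~ N(0, SD²), SD 0.5, 0.75, 1.16, 1.34; rule checked after six patients.
- Power model: p_i = s_i^exp(b), with s_i the initial rate.
- Logistic model: logit p_i = 3 + exp(b)·x_i, with x_i = logit(s_i) − 3.
- Likelihood: p for a DLT, 1 − w·p otherwise. Estimates are posterior means.

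Full follow-up (w = 1), lowest-level estimate across the four SDs:

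| Related deaths in 6 | Power | Logistic |
|---|---|---|
| 1 | 0.181–0.206; Level 3 closest to 0.35 | 0.172–0.182; Level 3 closest |
| 2 | 0.280–0.315; stays at 30 Gy at 4 of 4 | 0.313–0.335; stays at 2 SDs, 25 Gy at 2 |
| 3 | 0.351–0.448; stops at 2 of 4, else 25 Gy | 0.440–0.507; stops at 4 of 4 |

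After one death the one-step cap turns Level 3 into Level 2, which is 35 Gy. Under the power model the Level 3 estimate is 0.302–0.339, inside the 30–40% window. Under the logistic it is 0.282–0.298, so no level lies inside the window and the text does not clearly prescribe a dose.

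**4. Partial follow-up, one death.** Planned accrual is 36/20 = 1.8 months per patient. With even arrivals, patients 1 to 6 have 10.8, 9.0, 7.2, 5.4, 3.6 and 1.8 months of follow-up when patient 7 is assigned. The 6-month linear weights are 1, 1, 1, 0.9, 0.6, 0.3. The 75%/25% weights over 9 months are 1, 1, 0.85, 0.675, 0.45, 0.225. The table counts patient 7 going to 35 Gy in 24 cases (4 SDs × 6 positions of the death), power model:

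| Gap (months) | 6-month weights | 9-month weights |
|---|---|---|
| 1.8 | 24 | 24 |
| 1.5 | 24 | 18 |
| 1.2 | 20 | 6 |
| 1.0 | 15 | 2 |

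At 1.8 months the logistic model gives 24 and 20. With random arrivals averaging 1.8 months, the power model escalates in 76–92% of runs (6-month weights) or 55–80% (9-month weights), depending on SD. If the 40% rule may also act inside the run-in, these become 43–92% and 30–80%, because an early death can stop the trial first.

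**5. How likely is a related death?** The documents give no rate. At assumed true rates of 2%, 5% and 10%, 1 − (1 − p)^n gives 0.114, 0.265 and 0.469 for six patients, and 0.332, 0.642 and 0.878 for twenty.

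**The case against.** Counting grade 5 events as DLTs is an explicit choice and contradicts nothing in the plan. Escalating after one DLT in six is what a 35% target implies, and the estimates above would be the same for grade 3 diarrhea. They show ordinary CRM behavior, not harm caused by the missing hold. This stands, so the numbers are only an illustration that the 40% rule does not act as a death rule.

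Oversight is also fuller than the stopping rule suggests. At even 1.8-month gaps, patient 7 arrives about 10.8 months after patient 1. If the first enrollment is near activation, the QASMC will already have had a report, and a monthly investigator review will usually fall between patients. A reader might infer that a death could go unnoticed, or that the trial has no safety oversight. The documents do not support that: deaths are reported and shown separately from other DLTs. What remains is that none of these steps must be completed before the next start.

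The protocol also defers to IRB policies, an institutional monitoring plan and institutional guidelines. A hold may sit there. This limits confidence in the practical effect, but not the finding about the text.

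**Conclusion.** The point holds as a gap in the written rules. A related death within 6 months is one ordinary DLT, the only mandatory stop depends on the pooled lowest-level estimate, and no step in the documents holds the next start or requires a decision. This does not depend on any model.

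The size does. After one death in six fully followed patients, the lowest-level estimate is about 0.17–0.21 under both model families, so the 40% rule would not act. Escalation to 35 Gy is then possible, and at planned accrual it occurs in most cases if the rule is first checked after six. It is uncommon at faster accrual with the 9-month weights.

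Two stronger readings should be resisted. One is that the plan will always escalate after a death; accrual, weights, model and the reading of the run-in rule all change that. The other is that a fixed number of deaths is needed to stop the trial; after two or three deaths the result depends on a model the documents do not state.

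**What to change.** Add to Section 10.1.2 and to the Appendix F stopping-rule entry: any grade 5 event at least possibly related to study radiation holds new treatment starts until the QASMC has reviewed it, within a stated time that the sponsor sets, together with the current model output (posterior and DLT count by level), and has recorded a decision to continue, modify or close. Keep the 40% rule unchanged. This wording also covers a related death after month 6, which falls outside the DLT definition.

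The change is a short amendment using the existing investigator, statistician and committee, with the sample size still 20. The downside is a possible short accrual pause after such a death; the time limit keeps it from being open-ended. In this poor-prognosis population a possibly-related trigger could be used more than once, but deaths judged unrelated to study radiation would not trigger it. If institutional policy already requires such a review, stating it here costs almost nothing.

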10.2 Simulation and Sample Size Calculations

The TITE-CRM manual details methods for utilizing trial simulation in order to obtain estimated posterior probabilities on toxicity estimates. We utilized the simulation program to determine the efficacy of our trial and obtain estimates for needed sample size. While there is no exact power calculation for this type of trial, the effectiveness of the trial's sample size can be determined by looking at the stability of the posterior probability under different prior probabilities.

We ran 1000 simulations under various increasing and decreasing prior probability estimates utilizing the previously described rules and assumptions for this trial and saw sufficient stability in posterior probability estimates with a sample size of 20 patients with a run-in of 6 patients. Simulations showed that approximately 95% of the time the trial will come to completion and the MTD will fall between the 3rd and 5th dose level 89% of the time. Therefore, we will use a fixed sample size of 20 patients for this trial. The posterior probability distribution of these 1000 simulations follow in the next table.

Version 09/11/2025 page 41 of 63

Dose Level	Estimated	Mean
	initial	Posterior
	toxicity	toxicity (SD)
d-1	0.25	0.328 (0.434)
1	0.30	0.38 (0.453)
(Starting		
Dose)		
2	0.35	0.43 (0.463)
3	0.40	0.479 (0.464)

Summary of simulation with estimated posterior probabilities. SD, Standard Deviation

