10 STASTISTICAL CONSIDERATIONS

10.1 Phase I Methodology for Primary Endpoint

10.1.1 Background of TITE-CRM and trial rules

The Time-to-Event Continual Reassessment Method (TITE-CRM) proposed by Cheung and Chappell is an adaptive Phase I design (98). In a TITE-CRM clinical trial, patients enroll as they become available to be studied. Each participant is assigned to a dose level from a set of dose levels pre-defined by investigators and is monitored for DLTs over time. The design is adaptive in that the dose level assigned to a newly enrolled patient depends on the dose level assignments and dose limiting toxicity outcomes of the patients already in the study. A patient's observation period ends at the occurrence of a DLT or, if a DLT does not occur, after a fixed time T of follow-up. The trial ends when a fixed number of patients, n, have been observed. Once the final patient has been observed, the MTD can be estimated using the available data.

Version 09/11/2025 page 39 of 63

The TITE-CRM differs from the traditional CRM in that the estimation process is weighted to account for the proportion of the observation period that each currently enrolled patient has been observed. By not requiring complete observation before the enrollment of the next patient, new participants can be assigned a dose and begin evaluation as they become available, subsequently shortening the overall duration of the study.

The Biostatistics Unit at the University of Michigan Comprehensive Cancer Center has developed a program titecrm.sas for SAS 9 (SAS Institute, Inc.; Cary, NC) that makes all of the calculations necessary to determine dose allocation of a trial in real-time. They have also developed simulation programs that allow the user to determine the efficacy of the trial based on *a priori* estimates of the probabilities of toxicity and necessary sample sizes.

In order to properly utilize this type of trial, a few assumptions and many rules must be determined before the start of the trial. The main assumption that must be determined is how many different dose levels will be included in the trial and *a priori* estimates of the probability of a DLT at each of those dose levels. For this trial, we have 5 dose levels listed below $(d_1,...,d_5)$, with initial toxicity probability estimates $(p_1,...,p_5)$ ranging from 0.05 to 0.25, respectively. The following table shows the dose design with associated estimated probabilities of toxicity.

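### The simulation results that justify n = 20 refer to a 5th dose level, but the trial has four levels and two conflicting sets of initial DLT probabilities

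*Combined protocol and SAP*

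**What the plan says.** Section 10.1.1 states "For this trial, we have 5 dose levels listed below", with initial DLT probabilities "ranging from 0.05 to 0.25, respectively", and then announces: "The following table shows the dose design with associated estimated probabilities of toxicity". The table that follows has four levels (-1, 1, 2, 3) and no probability column.

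Section 10.2 reports 1000 simulations run "under various increasing and decreasing prior probability estimates". It says the authors "saw sufficient stability in posterior probability estimates with a sample size of 20 patients", that "approximately 95% of the time the trial will come to completion", and that "the MTD will fall between the 3rd and 5th dose level 89% of the time". The fixed sample size of 20 is drawn directly from these statements. The results table below them has four levels, with initial toxicity 0.25, 0.30, 0.35 and 0.40 and mean posterior toxicity (SD) of 0.328 (0.434), 0.38 (0.453), 0.43 (0.463) and 0.479 (0.464).

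Section 10.1.2 sets a 35% target, a 5% margin, a run-in of 6 patients, and a rule that if "the lowest dose level has a posterior probability higher than 40% then the trial will stop". It places the 30 Gy start two levels below the expected MTD; Section 10.2.1 places it one level below.

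**The concern.** The 95% and 89% figures, with the table, are the only quantitative support offered for 20 patients. One of them names a dose level the trial does not have, so a reader cannot tell which design was simulated.

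The initial DLT probabilities (the skeleton) matter beyond the sample size. They are an input to every dose assignment and to the 40% stopping rule. If the protocol carries two versions, the same patient data can give different decisions.

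**Working it through.** **1. Can the 95% and 89% be reproduced?** No. The documents do not give the model form, the prior SD, the true-toxicity scenarios or the accrual pattern. Monte Carlo error with 1000 runs is small: √(0.89×0.11/1000) = 1.0 percentage point and √(0.95×0.05/1000) = 0.7.

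**2. Level count and skeletons**

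| Place | Levels | Initial DLT probabilities |
|---|---|---|
| Schema; Section 1.7.1 | 4 | none given |
| 10.1.1, text | 5 | 0.05 to 0.25 |
| 10.1.1, table | 4 | none given |
| 10.2, text | a 3rd to 5th level | not listed |
| 10.2, table | 4 | 0.25, 0.30, 0.35, 0.40 |

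Read as labels, levels 4 and 5 do not exist. Read as rank order, there is no 5th. The two sets share only the value 0.25, the top of one and the bottom of the other. All of the first set lies below the 30-40% admissible range; three of the four values in the second lie inside it.

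**3. How far the figures depend on the unstated inputs.** I simulated the four-level design with the tabled skeleton, n = 20: 1000 trials in each of 32 settings (4 truths × prior SD 0.3 or 1.16 × weights linear over 6 months or 75% over 6 plus 25% over 3 × 30% floor on or off). I assumed a power model, 20 patients in 36 months, run-in of 6 at level 1 and one-level moves.

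| True DLT rates, levels -1, 1, 2, 3 | Completes | Level 2 or 3 chosen |
|---|---|---|
| 0.25, 0.30, 0.35, 0.40 (as tabled) | 51-99% | 27-67% |
| 0.10, 0.20, 0.30, 0.40 | 75-100% | 41-90% |
| 0.05, 0.10, 0.20, 0.35 | 92-100% | 37-99% |
| 0.35, 0.40, 0.45, 0.50 | 27-94% | 14-31% |

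These are illustrations, not bounds. A second set of runs that also allowed a one-parameter logistic model gave 38-61% completion at prior SD 1.16 with truth as tabled. One five-level setting with assumed truth 0.10, 0.18, 0.25, 0.35, 0.50 gave 95.3% and 89.1%. So figures near 95% and 89% are attainable with five levels, and some four-level scenarios come close. The documents do not say which applies.

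**4. Effect on the stopping rule.** Take the 6 run-in patients at level 1 with full follow-up and y DLTs. Model: p_i = s_i^exp(β), β ~ N(0, σ²). The posterior for β is proportional to p_1^y (1 − p_1)^(6−y) times the prior; the quantity tested is the posterior mean of p at level -1. The 0.05-0.25 set is spread evenly over four levels: 0.05, 0.117, 0.183, 0.25.

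| σ | First split at | Skeleton 0.25-0.40 | Skeleton 0.05-0.25 |
|---|---|---|---|
| 1.16 | 3 DLTs | 0.437 (stop) | 0.338 (continue) |
| 0.6 | 4 DLTs | 0.451 (stop) | 0.302 (continue) |
| 0.3 | 6 DLTs | 0.406 (stop) | 0.209 (continue) |

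Two other mappings of the lower set (0.05-0.20 and 0.10-0.25, in steps of 0.05) also continue at 3 DLTs with σ = 1.16 (0.356 and 0.391).

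**5. The SD column.** A quantity on [0, 1] with mean m has SD at most √(m(1 − m)).

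| Level | Mean | Tabled SD | Maximum SD | Ratio |
|---|---|---|---|---|
| -1 | 0.328 | 0.434 | 0.469 | 0.924 |
| 1 | 0.38 | 0.453 | 0.485 | 0.933 |
| 2 | 0.43 | 0.463 | 0.495 | 0.935 |
| 3 | 0.479 | 0.464 | 0.500 | 0.929 |

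Suppose these SDs describe spread between runs. Linear programming over all distributions on [0, 1] with the tabled mean and SD then gives:

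- The lowest-level posterior exceeds 0.40 in at least 27.5% of runs, so completion is at most 100 − 27.5 = 72.5%, against 95%.
- Level 2 exceeds 0.40 in at least 37.9% of runs. If level 3 is at or below 0.40, so is level 2. An MTD at level 2 or 3 is therefore possible in at most 100 − 37.9 = 62.1% of runs, against 89%.
- If the 30% floor is enforced, the limit is 14.6 + 16.3 = 30.9%.

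Between-run SDs in my 32 settings were 0.037 to 0.132, so the smallest tabled SD is 0.434/0.132 = 3.3 times the largest of mine.

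**The case against.** The 95% mentions no level count, and four-level designs with low true toxicity reach it: one re-run with truth 0.05, 0.10, 0.20, 0.35, linear 6-month weights and prior SD 1.16 gave 96%. That stands. The 95% is untraceable rather than contradicted, but it comes from the same simulations as the 89%.

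The 0.05-0.25 range may be leftover text. Only the table in 10.2 gives one value per existing level, and its 0.35 at level 2 fits a start one level below the expected MTD. This is plausible, but 10.1.1 states the other set in running prose as the design of this trial, and nothing withdraws it.

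The stopping example rests on an assumed model, prior SD and mapping. At prior SD 1.16 the decisions split only at exactly 3 DLTs in six patients; at 0.3 it takes six of six. So the conflict can change a decision, but how often is unknown.

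The SD argument is conditional, since the plan does not say what the column measures. The 72.5% limit also assumes no trial first crosses 40% after the 20th enrolment, which was rare in a re-run (at most 0.4%). With a plug-in estimate, between-run SDs reached 0.15 and the ratio falls to about 2.9. The tabled SDs remain far larger.

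Finally, the start-position conflict is one of wording: both sections give 30 Gy.

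**Conclusion.** The concern holds and must be fixed. Five levels against four, and 0.05-0.25 against 0.25-0.40, are contradictions on the page that need no modelling. The 89% cannot be matched to the four-level design, and the 95% cannot be traced to any stated inputs. The sample size of 20 is unsupported as written; it is not shown to be wrong.

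The dose-assignment and stopping model is specified two ways, and under the stated assumptions this can reverse a stopping decision at the end of the run-in. The SD column either contradicts the completion and stability claims (if between-run) or is wrong or mislabelled (if not). The simulated ranges and run-in posteriors depend on my assumed model, prior SD, accrual and mapping; the counts and the maximum-SD ratios do not.

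**What to change.** - Reconcile 10.1.1 (text and table), 10.1.2, 10.2 and 10.2.1 to one set of levels, one initial probability per level, and one statement of where the start lies relative to the expected MTD. Which levels apply is for the sponsor to settle.
- State the model form, the prior SD, and whether the 30% floor applies when the MTD is selected.
- Re-run the simulations with exactly those levels, the 35% target, the final weight function (the present one spans 6 + 3 = 9 months against a 6-month DLT window), the run-in and the stopping rule.
- Replace the 95%, the 89% and the table with results for listed true-toxicity scenarios: the probability of selecting each level, of stopping early and of declaring no MTD. Say what the SD column measures, or correct it.
- State what n = 20 delivers under those scenarios. The number can stay if the sponsor accepts the result.

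The cost is one simulation re-run and a text amendment. Restating what n = 20 delivers adds no patients, though the reported probabilities may be less favourable than those now in the plan.
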